8 RESPONSE MEASURES AND SUMMARY OF DATA COLLECTION METHODS

8.1 Safety Measures

The following safety assessment measures will be conducted as indicated in Section 7.1, Time and Events Table.

- Physical examination
- Vital signs (blood pressure, pulse rate, respiratory rate, and temperature)
- Laboratory tests (hematology, chemistry, urinalysis) and pregnancy testing in FOCBP
- Collection of AEs
- Local tolerability assessments

8.1.1 Physical Examination

Physical examination will include assessments of the head, eyes, ears, nose, throat, skin, thyroid, neurological, lungs, cardiovascular, abdomen (liver and spleen), lymph nodes, and extremities. Height and weight will also be measured and recorded.

8.1.2 Vital Signs

Subjects should be seated for ≥2 minutes prior to measurements. Pulse rate (bpm) will be counted over 60 seconds. Blood pressure (mmHg) will be measured with a sphygmomanometer.

Vital sign measurements will include systolic and diastolic blood pressure, pulse rate, respiratory rate, and temperature.

8.1.3 Clinical Laboratory Assessments

Hematology, clinical chemistry, urinalysis, and additional parameters to be tested are listed below:

Hematology

Trematorogy		
Platelet count	RBC Indices:	Automated WBC Differential:
Red blood cell (RBC) count	Mean corpuscular volume (MCV)	Neutrophils
White blood cell (WBC) count	Mean corpuscular hemoglobin (MCH)	Lymphocytes
Reticulocyte count	Mean corpuscular hemoglobin concentration (MCHC)	Monocytes
Hemoglobin		Eosinophils
Hematocrit		Basophils

Clinical Chemistry

Blood urea nitrogen	Chloride	Alkaline phosphatase
Creatinine	Aspartate aminotransferase (AST)	Total and direct bilirubin
Sodium	Alanine aminotransferase (ALT)	
Potassium	Gamma glutamyl transferase (GGT)	

Routine Urinalysis

Bilirubin, color, appearance, glucose, ketones, leukocyte esterase, nitrite, occult blood, pH, protein, specific gravity, and urobilinogen

Microscopic examination (if blood or protein is abnormal)

Other Screening Tests

Urine Pregnancy Test (females of childbearing potential* only, using UPT tests provided by the Sponsor.)

^{*} Females of childbearing potential for this study includes any female capable of becoming pregnant who has not undergone successful surgical sterilization (hysterectomy, bilateral tubal ligation [≥6 months prior to baseline], or bilateral oophorectomy) or is not postmenopausal (defined as amenorrhea ≥12 consecutive months).

All results will be reported and must be reviewed by the Investigator or designee. Abnormal results shall be assessed for clinical significance. Repeat laboratory testing may be requested at the discretion of the Investigator. If an AE should require laboratory testing, the results of the test should be obtained by the investigative site and filed in the subject's documentation.

8.1.4 Adverse Events

Adverse events (AEs; see Section 9.2) will be collected for all untoward medical occurrences in a subject entered into this clinical study (e.g., signed consent), whether or not a pharmaceutical product has been administered. Any event, including local tolerability assessments (see Section 8.1.5), that requires specific treatment, results in interruption of treatment, or results in discontinuation of the subject from the study will also be reported as an AE.

Care will be taken not to introduce bias when detecting AEs and/or SAEs. Open-ended and non-leading verbal questioning of the subject is the preferred method to inquire about AE occurrence.

Appropriate questions include:

- "How are you feeling?"
- "Have you had any (other) medical problems since your last visit/contact?"
- "Have you taken any new medicines, other than those provided in this study, since your last visit/contact?"

8.1.5 Local Tolerability Assessments

Local tolerability assessments (see Appendix 5) will be evaluated through assessment of symptoms at the drug application site. These assessments are to be performed for both axillae individually. Subject assessments will be made prior to the Investigator assessments.

Subject Local Tolerability Assessments: Subjects will be queried about whether any symptoms occurred at the study drug application site within the previous 24 hours and further whether any such symptoms persisted longer than 1 hour following study drug application. Standardized scales will be used to describe specifically the severity of any burning, stinging, or itching.

Investigator Local Tolerability Assessments: Investigators will observe for the existence of any significant local symptoms at the study drug application site. Significant local symptoms are defined as those not ordinarily observed following application of a topical product. Standardized scales will be used to describe specifically the severity of any erythema or scaling.

Local tolerability signs and symptoms that result in a subject requiring a concomitant therapy, interruption of treatment, or discontinuation from the study, will be reported as AEs.

8.1.6 Subject Assessments

Subjects must complete ALL self-assessments while at the clinic (i.e., HDSM-Ax, DLQI, PGI-S, PGI-C) prior to assessments being made by the Investigator. Please see Appendix 2 and Appendix 3 (HDSM-Ax by age; also includes PGI-S and PGI-C) and Appendix 4 (DLQI) for a full description of these assessments. Subjects will also have the option to complete an End of Study Survey. The HDSM-Ax, DLQI, PGI-S, and PGI-C assessments, as well as the optional End of Study Survey, will be collected electronically using a tablet device. Site personnel will be trained and a separate electronic clinical outcomes assessment (eCOA) manual will be supplied.

8.1.7 Allergic Contact Dermatitis (Skin Sensitization) Assessment

Allergic contact dermatitis (ACD), as an AE, may manifest as moderate/severe pruritis and moderate/severe erythema with or without vesicles/bullae.

In the case of a suspected AE of ACD, the medical monitor should be contacted to discuss the case. If the medical monitor and the investigator agree that the AE is suggestive of ACD, the assigned treatment should be withheld, the AE documented, and treated, if required, by concomitant therapy that can include topical corticosteroids at the discretion of the investigator. Once the AE of ACD is resolved, in the opinion of the investigator, any concomitant therapy for this AE should be stopped, and the assigned treatment should be restarted (i.e., re-challenge exposure) after discussion with the medical monitor. If there is recurrence, an AE of ACD is confirmed and should be documented as an AE that is related to the assigned treatment.

8.2 Summary of Methods of Data Collection

This protocol will utilize validated 21 Code of Federal Regulations (CFR) Part 11 compliant electronic data capture (EDC) software and eCOA software to collect required study data. The Investigator must ensure that data are properly recorded on each subject's eCRFs, eCOAs, and related documents. When changes or corrections are made in the eCRF, the EDC systems will maintain an audit trail of the person making the changes, the date and time of the change, and the reason for the change. Only individuals listed on the Delegation of Responsibilities Log with responsibility for eCRF completion may make entries in the eCRFs.

The Investigator or physician Sub-Investigator must electronically sign and date each subject's eCRF for each timepoint completed. Individuals who will be providing electronic signatures must first submit documentation with a handwritten signature acknowledging that their electronic signature is a legally binding equivalent to their handwritten signature.

8.3 Efficacy Measures

The following assessment measures will be conducted to evaluate the long-term efficacy of sofpironium bromide gel, 15% as indicated in the Procedures Section 7.1:

- HDSM-Ax as measured by the subject
- GSP as measured by the Investigator
- DLQI as measured by the subject (for subjects ≥ 17 years of age)
- Patient Global Impression Scales; Severity (PGI-S) and Change (PGI-C)

9 ADVERSE EVENTS (AE) AND SERIOUS ADVERSE EVENTS (SAE)

9.1 Safety Evaluations

The Investigator is responsible for the appropriate medical care and the safety of subjects who have entered this study. The Investigator must document any AE experienced by subjects who have entered this study and report all SAEs to the CRO (see Section 9.3.1). Contact information for the Sponsor's Medical Monitor is provided on the protocol cover page.

9.2 Adverse Events

9.2.1 Definitions of Adverse Events

According to 21 CFR Parts 312.32 and 320.32 (IND Safety Reporting, Applicability of Requirements Regarding an "Investigational New Drug Application"), Food and Drug Administration (FDA) Guidance for Industry (Investigational New Drug Safety Reporting Requirements for Human Drug and Biological Products and Safety Reporting Requirements for Bioavailability and Bioequivalence Studies in Humans) (Federal Register/Vol. 75, No. 188/September 29, 2010) and International Council on Harmonisation (ICH) E2A (Clinical Safety and Data Management: Definitions and Standards for Expedited Reporting):

An adverse event (AE) means any untoward medical occurrence associated with the use of a drug in humans, whether or not considered drug related.

A suspected adverse reaction (SAR) means any AE for which there is a reasonable possibility that the drug caused the AE.

The following information should be considered when determining whether or not to classify a test result, medical condition, or other incident as an AE:

Adverse events will be recorded from the time of informed consent.

Abnormal laboratory values should not generally be recorded as AEs unless an intervention is required, the laboratory abnormality results in an SAE, the lab abnormality results in study termination or interruption/discontinuation of study treatment, or the lab abnormality is associated with clinical signs or symptoms. When recording an AE resulting from a laboratory abnormality, the resulting medical condition rather than the abnormality itself should be recorded (e.g., record "anemia" rather than "low hemoglobin").

Complications that occur in association with a protocol-mandated intervention (e.g., invasive procedures such as biopsies) should be recorded as AEs.

Whenever possible, the Investigator should group signs or symptoms that constitute a single diagnosis under a single event term. For example, cough, rhinitis, and sneezing might be grouped together as "upper respiratory tract infection." If possible, abnormal laboratory results that meet the definition of an AE (see above) should be reported as a clinical diagnosis rather than the abnormal value itself (e.g., "anemia" rather than "decreased blood count").

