5.2 Instructions for Use and Administration of Investigational Product

Investigational product kit cartons will be provided to each site and will include one individual plastic pump container per each carton. Each carton will also contain 2 applicators. An investigational plastic pump container will contain sufficient drug product for a 28-day treatment period.

Each carton will have a unique identifier number printed on the label. The pump container label will display the same unique identifier number.

Each subject will be randomized via an Interactive Response Technology (IRT) system to receive either sofpironium bromide gel, 15%, or vehicle gel (placebo) to topically apply, once daily at bedtime, to each axilla using the supplied applicators for 42 consecutive days. Instructions on the use of the IRT system will be provided in a separate manual.

Subjects will be instructed to apply the investigational gel product to each axilla using all the gel expressed from **one full actuation** of the pump per each axilla dose application. Each full actuation of the pump corresponds to approximately 86.5 mg of sofpironium bromide in the 15% investigational product.

The subject will apply all doses of investigational product at night, prior to going to bed, using the supplied applicators. Subjects will apply their first dose of gel prior to bedtime on the night of their Baseline Visit. The subject will be instructed to continue applying the investigational product each night with the last application to occur the night before attending the end of treatment evaluation (i.e., Visit 12). Subjects should wash the applicator each night after dosing. Two applicators are provided in each kit to compensate for loss or damage during handling; it is not necessary to use all the applicators over the specified dosing interval.

To ensure accurate dosing, the study staff will be instructed to first prime and then weigh each pump container before dispensing to the subject. Priming is accomplished by fully pressing the pump for five (5) sequential actuations; the dispensed gel from these 5 priming actuations is considered waste and should be discarded.

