9.2.1.2 Assessment of Adverse Events

For each AE, the start and resolution dates, intensity, seriousness (i.e., whether the event meets the definition of an SAE [Section 9.3.1]), relationship of the event to the study drug, action taken regarding study drug, and outcome of the event will be documented on the eCRF.

Intensity

The following definitions should be used to assess and grade AE intensity, including laboratory abnormalities judged to be clinically significant.

Severity	Grade	Description	
Mild	1	Awareness of sign or symptom, but easily tolerated	
Moderate	2	Discomfort enough to cause interference with usual activity	
Severe	3	3 Incapacitating with inability to work or do usual activity	

Note: a severe adverse event is not necessarily serious.

Relationship

The relationship of an AE to study drug should be assessed using the guidelines presented in the table below. An AE for which there has been no causal relationship reported will require follow-up to determine causality.

Adverse Event Relationships to Study Drug

Degree of Certainty	Description
Definitely Related	An event that follows a reasonable temporal sequence from administration of the test article; that follows a known or expected response pattern to the test article; and that is confirmed by improvement on stopping or reducing the dosage, and reappearance of the event on repeated exposure (re-challenge).
Probably Related	An event that follows a reasonable temporal sequence from administration of the test article; that follows a known or expected response pattern to the test article; and that is confirmed by improvement on stopping or reducing the dosage of the test article; and that is unlikely to have been caused by concurrent/underlying illness or other drugs, procedures, or other causes.
Possibly Related	An event that follows a reasonable temporal sequence from administration of the test article; that follows a known or expected response pattern to the test article; but may have been caused by concurrent/underlying illness, other drug, procedure, or other causes.
Unlikely Related	An event that does not follow a reasonable temporal sequence from administration of the test article; that does not follow a known or expected response pattern to the test article, or most likely was caused by concurrent/underlying illness, other drug, procedure, or other causes, because of their known effects.

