9.6 Other Safety Measures

Safety will also be assessed by physical examinations, laboratory tests, and measurement of vital signs assessed as indicated throughout the study schedule. Clinically significant changes in these parameters may be captured as adverse events.

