## 9.4 Clinical Laboratory Evaluation

Safety laboratory parameters (hematology, chemistry, urinalysis) will be collected at the Screening Visit and EOT Visit. Urine pregnancy results will be collected at visits 1, 4, 8, and 12 (EOT). Laboratory parameters will be presented in Systeme International (SI) units and descriptively summarized for values at each visit and for changes from baseline at each subsequent visit. Unscheduled visits and early termination visits will be included.

Laboratory parameters to be summarized and listed include hematology, clinical chemistry, and routine urinalysis. Urine pregnancy test results will be listed only.

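### Protocol 9.2.1, 9.2.1.2 and 9.6 do not agree on when a clinically significant laboratory value is an AE, and the chemistry and hematology tables cannot show how many subjects per arm had one

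*Protocol*

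**What the plan says.** **Recording.** Protocol 9.2.1 sets the general position: "Abnormal laboratory values should not generally be recorded as AEs unless an intervention is required, the laboratory abnormality results in an SAE". The list continues with study termination or interruption or discontinuation of study treatment, and ends "or the lab abnormality is associated with clinical signs or symptoms". That makes four triggers, and the Investigator's judgement of clinical significance is not one of them.

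Protocol 9.2.1.2 introduces the intensity scale: "The following definitions should be used to assess and grade AE intensity, including laboratory abnormalities judged to be clinically significant". Its lowest grade, mild, is defined as "Awareness of sign or symptom, but easily tolerated".

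Protocol 9.6, covering physical examination, laboratory tests and vital signs, says: "Clinically significant changes in these parameters may be captured as adverse events".

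Protocol 8.1.3 requires the judgement on which the last two passages turn: "Abnormal results shall be assessed for clinical significance".

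**Timing.** Safety laboratories are scheduled at Visit 1 and Visit 12 only (Protocol 7.1, SAP 9.4). Dosing continues each night, "with the last application to occur the night before attending the end of treatment evaluation", which is Visit 12.

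**Tabulation.** SAP 9.4 has laboratory parameters "descriptively summarized for values at each visit and for changes from baseline at each subsequent visit". Protocol 10.4 names the statistics: mean, SD, median, minimum and maximum. Tables 14.3.4.1 (chemistry), 14.3.4.2 (hematology) and 14.3.4.3 (continuous urinalysis) are titled as mean and mean change. Table 14.3.4.4 shows categorical urinalysis values by visit, which SAP 3.1 would present as n (%). Individual results go to listings 16.2.8.1 to 16.2.8.3.

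**The concern.** A site that finds a clinically significant abnormality at the end of treatment, in a subject who feels well and needs no intervention, can act on any of three passages and reach different answers. The TEAE tables count only what was recorded. If the site follows 9.2.1, the subject is absent from them, and the chemistry and hematology tables have no line for the number of subjects out of range or judged clinically significant. The Investigator's judgement is required by 8.1.3, but no listed table uses it.

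What is at stake is the by-arm comparison of laboratory safety, in a trial whose first listed objective is safety and local tolerability and which plans no data monitoring committee (SAP 12). Different practice between sites would also make the laboratory-related TEAE counts harder to interpret.

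**Working it through.** The plan states no figure on this point, so there is none to reproduce. The check sets the passages side by side.

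**Step 1. One case through the three recording rules.** Take a Visit 12 chemistry value that the Investigator judges clinically significant. The subject has no signs or symptoms, no intervention is needed, there is no SAE, and the subject completes follow-up.

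- Under 9.2.1, none of the four triggers is met, so the value is generally not an AE.
- Under 9.2.1.2, it is a laboratory abnormality judged clinically significant, which the section includes among the things to be graded as AEs. A site can reasonably take this to mean it is one.
- Under 9.6, it may be captured, with no criterion for when.

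**Step 2. Can the triggers be met at Visit 12?** The only scheduled post-baseline sample is drawn the morning after the last application. A result from it comes too late to interrupt or discontinue treatment, so that part of the third trigger is in practice unavailable for scheduled samples. Intervention, SAE and symptoms remain open. So does study termination, since the Day 57 visit is still to come. The gap is therefore limited to values that meet none of these.

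**Step 3. If recorded, can it be graded?** The mild grade needs awareness of a sign or symptom. The moderate and severe grades are worded as interference with usual activity and incapacity. A symptom-free laboratory AE fits none of them. SAP 9.2 tabulates TEAEs by highest severity and has a category for unknown severity, where such events could end up.

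**Step 4. If not recorded, where does it appear?**

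| Output | Shows the value? | Counts the subject by arm? |
|---|---|---|
| TEAE tables | No | No |
| Tables 14.3.4.1 to 14.3.4.3 | Only within the summary statistics, at most as the minimum or maximum | No |
| Table 14.3.4.4 | Urinalysis categories only | By category, without clinical significance |
| Listings 16.2.8.1 to 16.2.8.3 | Yes | No |

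**Step 5. Would the mean show it?** This is an illustration only. The documents give neither the number of affected subjects nor the size of the rise, so both are assumed. With 175 per arm (Protocol 2), let *k* subjects in one arm each rise by *r* SD.

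- Shift in arm mean = *k* × *r* / 175, in SD.
- Standard error of the difference in means = √(2/175) = 0.107 SD.

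| *k* | *r* = 3 SD | *r* = 10 SD |
|---|---|---|
| 1 | 3/175 = 0.017 SD (0.16 SE) | 10/175 = 0.057 SD (0.53 SE) |
| 3 | 9/175 = 0.051 SD (0.48 SE) | 30/175 = 0.171 SD (1.60 SE) |
| 5 | 15/175 = 0.086 SD (0.80 SE) | 50/175 = 0.286 SD (2.67 SE) |

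One to three affected subjects would be hard to see in a mean-change table. Five with very large rises might be visible, but a mean cannot say whether five subjects or many were responsible.

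**The case against.** **The conflict is softer than it looks.** Section 9.2.1 is guidance and says *generally*. Section 9.2.1.2 starts from events already being documented as AEs, so its sentence can be read as telling sites how to grade a laboratory abnormality that already qualifies. On that reading it is not a competing recording rule, and the *may* in 9.6 is compatible with 9.2.1. This reading is tenable. It does not settle the matter, because the text does not say which reading is meant, and on it clinical significance has no defined role in recording.

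**Not all laboratory data go uncounted.** A reader might infer that no laboratory table counts subjects. The SAP does not support that: Table 14.3.4.4 counts urinalysis categories by visit. The point is confined to chemistry, hematology and continuous urinalysis, and to clinical significance throughout.

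**Nothing is hidden.** The values are in the by-subject listings and contribute to the minimum and maximum, and SAP 9.4 includes unscheduled and early-termination results. This stands: such subjects are uncounted, not unreported. The detailed table specifications are in a separate document not available here, so the finding rests on the SAP text and the table titles.

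**Vital signs.** A reader might extend the point to vital signs, since tachycardia is a named risk and Table 14.3.6.4 is also mean and mean change. The AE restriction in 9.2.1 covers laboratory values only. An untoward vital-sign change falls under the general AE definition, and anticholinergic TEAEs have their own tables and listing. Only the *may* in 9.6 touches vital signs, so the extension is not supported.

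**No laboratory risk is named, and shift tables are a matter of preference.** The background section identifies no specific laboratory hazard, and leaving out shift tables contradicts nothing in the plan. That limits the weight of the point but leaves the misaligned wording in place.

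**Conclusion.** The point holds in a limited form. The three protocol sections are not aligned. A clinically significant chemistry or hematology value at Visit 12 that meets none of the four triggers may or may not become an AE, depending on the section a site follows. When it does not, no listed table counts that subject by arm.

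The size cannot be stated, because the documents give no rate of such values. The mean-shift figures above rest on assumed numbers and show only that a mean cannot replace a count. No efficacy conclusion is affected. This is worth correcting because the change is cheap and safety is a stated objective; it is not evidence that harm would be concealed.

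The conclusion assumes that the listed table titles describe the table content, and that sites could reasonably follow any of the three sections.

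**What to change.** 1. **Protocol 9.2.1, 9.2.1.2 and 9.6:** state one recording rule for laboratory abnormalities judged clinically significant, and use it in all three places. If 9.2.1.2 is meant only to grade abnormalities that already qualify as AEs, say so there.
2. **Protocol 9.2.1.2:** make the intensity scale usable for a symptom-free laboratory AE, so that such events do not fall into the unknown-severity category.
3. **SAP 9.4:** add by-arm shift tables from Visit 1 to Visit 12 (below, within, above the reference range) for chemistry and hematology. These do not depend on how sites applied the AE rule. SAP 9.3 already plans shift tables for local tolerability, so the format is in use.
4. **SAP 9.4:** if the Investigator's clinical-significance judgement is in the database, add the number of subjects per arm with a clinically significant Visit 12 result. The documents do not say whether it is entered in the eCRF; if it is held only in source records, this count would need extra data collection.

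Counts of subjects with marked vital-sign changes are optional and not part of this correction.

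**Cost:** wording changes in the protocol and a few more tables. The shift tables use results already collected, assuming reference ranges come with them. AE counts would rise slightly if the single rule makes clinical significance sufficient for an AE. SAP 1 allows changes to the planned analyses to be documented before database lock.
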